1.3 IL-23 and GVHD

Studies in our laboratory using preclinical murine bone marrow transplantation models have demonstrated that IL-23 has a unique and selective role in the induction of colonic inflammation during acute GVHD and serves as a critical mediator linking conditioning regimen-induced mucosal injury and lipopolysaccharide (LPS) translocation to subsequent proinflammatory cytokine production and GVHD-associated pathological damage. 11,22 Specifically, transplantation of IL-23-deficient marrow grafts or administration of a p19-specific antibody significantly reduced the severity of acute GVHD, which was attributable to the preferential reduction in colonic GVHD, and a decrease in the production of proinflammatory cytokines within this tissue site. Secretion of IL-23 by donor, and not host, APCs was shown to be a critical event in the induction of GVHD of the colon. In subsequent studies, we identified that the proinflammatory effects of IL-23 were mediated through CD4⁺ T cells that expressed the IL-23 receptor.²³ Specifically, these studies identified a unique colitogenic CD4⁺ IL-23R⁺ T-cell population that constitutively expresses the β2 integrin, CD11c, has a biased central memory phenotype and memory T-cell transcriptional profile, possesses innate-like properties by gene expression analysis, and has increased expression of the gut-homing molecules, α4β7 and CCR9. Adoptive transfer of these cells resulted in increased overall mortality, proinflammatory cytokine production and pathology specifically in the colon. Collectively, these findings defined a novel organ-specific role for IL-23 in the pathophysiology of GVHD and demonstrated that IL-23 could direct tissue-specific pathology within the context of a systemic inflammatory disorder. Moreover, additional studies demonstrated that blockade of the IL-23 signaling pathway did not abrogate the graft-versusleukemia effect when tested in both acute and chronic models of leukemia.²³ Thus, targeting the IL-23 pathway for GVHD prevention in murine models resulted in separation of GVH and GVL reactivity. Thus, with a series of publications in well-characterized mouse models, we believe that we have established that IL-23 has a pivotal role in the pathophysiology of GVHD in the GI tract. In addition, there have been a number of studies that have suggested that donors with IL23R polymorphisms which result in attenuated IL-23 secretion have a protective effect on the occurrence of moderate-to-severe acute GVHD in transplant recipients.²⁴

1.4 Tildrakizumab

Tildrakizumab (IluymaTM) is a humanized monoclonal antibody that specifically binds to the IL-23p19 subunit of IL-23 to neutralize its function.²⁵ The drug has been evaluated in clinical trials for patients with moderate to severe psoriasis with good effect.^{25,26} The drug was well tolerated, with maximum-tolerated dose (MTD) of 10 mg/kg⁻¹ once monthly. The responses were achieved

at all dose level (0.05-10 mg/kg⁻¹), maximum responses were achieved at dose level 3 and 10 mg/kg⁻¹.

The most common adverse events reported were headache, nasopharyngitis, upper respiratory infection, and cough. There was no dose increase related adverse events. Among the serious adverse events reported was convulsion, which was attributed secondary to tildrakizumab, occurred 17 days after the 10 mg/kg⁻¹ doses, but there were several reported confounding factors; alcohol consumption, lack of sleep and use of benzodiazepines. In terms of pharmacokinetic, the drug had slow systemic clearance with long half-life of around three weeks. Another significant finding of the study was that the IL-23p19 expression almost completely disappeared from the affected tissue after tildrakizumab treatment, suggesting that the drug possesses direct effect on IL-23 producing cells. Based on this data, tildrakizumab was FDA approved for treatment of moderate to severe plague psoriasis in March 2018.

1.5 Tildrakizumab and Treatment of GVHD

To date, tildrakizumab has not been tested for prevention or treatment of GVHD but based on aforementioned data suggesting a pivotal role for IL-23 in the pathophysiology of GVHD, coupled with the very favorable safety profile of tildrakizumab; we propose to conduct a phase II study evaluating the efficacy of tildrakizumab plus standard immunosuppressive therapy in preventing GVHD in patients undergoing a myeloablative HSCT. The FDA approval for use of this agent in patients with plaque psoriasis, with a well-reported safety profile, justifies not embarking on a phase I study in this population. However, as we were well aware that patients undergoing MAC alloHCT patients represent a uniquely vulnerable patient population with potential for unexpected and potentially life-threatening adverse effects, we initially proposed a safety run-in phase of six patients to ensure these patients appropriately engrafted and did not experience any unexpected adverse events before proceeding to the full phase II study.

1.6 Correlative Studies

Given the known cytokine dysregulation that is seen in the setting of allogeneic HSCT, especially in acute GVHD,²⁷ we intend to perform correlative studies to understand the impact of anti-IL-23 antibody treatment on the proinflammatory cytokine milieu that is typically seen post-allogeneic HSCT. This testing may help us better understand the changes that are happening within the immune system to inhibit graft-versus-host disease (GVHD).

1.7 Studies of the Microbiome in Transplant Patients

The microbiome, consisting of a varied community of microbes (bacteria, viruses, fungi, microeukaryotes, and sometimes multicellular parasites), exists in niches across the human body. The skin, lung, nares, vagina, and gastrointestinal tract are among the most heavily colonized, with the largest number of microorganisms inhabiting the colonic lumen. While the majority of the over trillion organisms that live within a healthy human colon are nonpathogenic members of the phyla Firmicutes, Bacteroidetes, Actinobacteria, and Proteobacteria, alterations in the balance of these microorganisms have been associated with adverse outcomes ranging from GVHD and infection to relapse post-HCT. ²⁸ This clinical association between intestinal microorganisms and HCT outcomes has been investigated for decades and has informed the still controversial practices of infection prophylaxis, gut decontamination, the "neutropenic diet," and isolation of patients in laminar air flow rooms. Single-institution studies have demonstrated that low microbial diversity in the stool after allogeneic HCT is associated with poor survival. ^{29,30}

Version Date: 10/31/2022

Additionally, specific alterations have been associated with increased risk of acute GVHD, infectious outcomes and most recently, relapse. 31-33 While these findings are compelling, the generalizability of these proposed microbial biomarkers is unclear. This is particularly important as there is known geographic variation of the intestinal microbiome and practice variability in antibiotic use for prophylaxis and treatment from institution to institution, in part due to different antibiograms.

Novel methods in microbiome research are likely to facilitate translational breakthroughs these methods allow (1) detailed taxonomic classification of microorganisms at the strain level, (2) metabolic characterization of the small molecules and proteins that a microbial community makes, (3) measurement of microbial genomic evolution in clinical time courses, and (4) culturing of previously fastidious organisms from the microbiome for in vitro investigation and cultivation as potential therapeutic live bacterial clinical interventions. Given recent reports suggesting that alterations in the microbiome can impact the efficacy of immunologic therapies. it is imperative that the link between the microbiome and transplant outcomes is investigated. 34,35

1.7.1 Microbiome and Outcomes after Allogeneic Transplantation using Tildrakizumab as **GVHD Prophylaxis**

The study will test the secondary hypothesis that the use of IL-23 blockage (tildrakizumab), which has been shown to lower gastrointestinal GVHD rates, preserves the gut microbiome diversity (determined by 16s rRNA sequencing analysis of the sequential stool sample collected pre- and post-transplant until neutrophil engraftment). Additional analyses on patient samples will be conducted to answer the key question concerning the impact of the gut microbiome on transplant outcome. Aliquots preserved additionally will establish a cohort of stool samples collected prospectively for future sequencing by shotgun metagenomic sequencing and metabolomic analysis. Previous GVHD prophylaxis studies performed at this institution have also evaluated microbiome diversity in this setting. Continuing these important exploratory evaluations will help to add to our knowledge base in this arena and will contribute importantly to future research.

2 HYPOTHESIS, OBJECTIVES, AND ENDPOINTS

In this study, we hypothesize that IL-23 inhibition through repeated treatment with tildrakizumab, when added to standard GVHD prophylaxis, will result in an improvement in GVHD-free relapse-free survival (GRFS) for adult patients undergoing a myeloablative allogeneic HSCT for hematologic malignancies.

2.1 Primary Objectives

The primary endpoint of this trial is to determine the probability of GVHD-free relapse-free survival (GRFS). An event for this outcome is defined as either grade III-IV acute GVHD, systemic therapy-requiring chronic GVHD, relapse, or death at 12 months after matched related/unrelated donor peripheral blood HSCT using myeloablative conditioning regimen. Patients who are alive without GVHD will be censored at the last follow-up.

Version Date: 10/31/2022

2.2 Secondary Objectives

- Cumulative incidence of mild, moderate and severe chronic GVHD according to the NIH. criteria and limited or extensive GVHD by conventional criteria.
- Cumulative incidence of grade II–IV acute GVHD at days 100 and 180.
- 3. Cumulative incidence of grade III–IV acute GVHD at days 100 and 180.
- Probability of lower GI tract GVHD.
- 5. Incidence of primary and secondary graft failure.
- 6. Probability of non-relapse mortality (NRM) post HSCT.
- 7. Cumulative incidence of relapse/progression of the primary malignancy.
- 8. Probability of overall survival (OS) post HSCT.
- 9. Assess the pharmacokinetic (PK) profile of multi-dose tildrakizumab.
- 10. Incidence of infections.
- 11. Donor cell chimerism.
- 12. Effect of GVHD prophylaxis on gut microbiome diversity: difference in level of microbiome diversity during transplant and association of baseline gut microbiome diversity with development of aGVHD, cGVHD and overall survival.

2.3 Rationale for the Outcome Measures Selection

Ample evidence suggests that IL-23 has a pivotal role in the pathophysiology of GVHD and preclinical studies suggest that blocking the IL-23 pro-inflammatory pathway can prevent GVHD. In this study, we will treat patients with tildrakizumab, which is a humanized monoclonal antibody that specifically binds to the IL-23p19 subunit of IL-23. We hypothesize that targeting IL-23 will reduce the incidence of GVHD and improve morbidity and mortality after transplantation.

2.4 Primary Endpoint

The primary endpoint of this trial is GRFS. An event for this outcome is defined as grade III-IV acute GVHD, chronic GVHD requiring systemic therapy, relapse or death. Patients who are alive without GVHD will be censored at the last follow-up.

2.5 Secondary Endpoint(s)

1. Chronic GVHD

The cumulative incidence of chronic GVHD by NIH Consensus criteria (Appendix 2) will be determined. Development of chronic GVHD will be considered an event for this endpoint. The highest grade of chronic GVHD will be recorded. In addition, the time of onset of chronic GVHD and the time to highest chronic GVHD grade will be recorded. Death but not disease relapse will be considered a competing event.

2. Acute GVHD

Cumulative incidences of grades II–IV and III–IV acute GVHD will be determined at day +100 and day +180 post-HCT. Acute GVHD will be graded according to Appendix 2. The time of onset of grade II-IV acute GVHD and time to development of the highest grade until day +180 will be recorded. Development of acute GVHD will be considered an event for this endpoint. Death but not disease relapse will be considered a competing event.

MCW Protocol No: PRO00035737 23 Version No. 7

3. Graft failure

Graft failure will be assessed as a secondary endpoint, including primary and secondary graft failure. Primary graft failure is defined as no neutrophil recovery to > 500 cells/uL by day 28 post-HCT. Secondary graft failure will be assessed according to neutrophil count after initial hematologic recovery. Secondary graft failure is defined as initial neutrophil engraftment followed by subsequent decline in absolute neutrophil counts <500 cells/µL, unresponsive to growth factor therapy, but cannot be explained by disease relapse or drugs.

4. Hematopoietic recovery

Hematopoietic recovery will be assessed according to neutrophil and platelet counts recovery after HSCT. Neutrophil recovery or engraftment is defined as achieving an absolute neutrophil count (ANC) ≥500/mm³ for three consecutive measurements on three different days. The first of the three days will be designated the day of neutrophil engraftment. The competing event is death without engraftment. Platelet recovery is defined by either the first day of a sustained platelet count >20,000/mm³ for three days with no platelet transfusion in the preceding seven days. The first day of sustained platelet count above these thresholds will be designated the day of platelet engraftment.

5. Non-relapsed Mortality (NRM)

NRM is defined as death after alloHCT without relapse. The cumulative incidence of NRM will be estimated at day +100 and one year after alloHCT. An event for this endpoint is death without evidence of disease progression or relapse. Disease progression or relapse will be considered a competing event.

6. Disease Relapse or Progression

Relapse is defined by either morphological, cytogenetic or radiologic evidence of the pretransplant hematologic malignancy. Institution of any therapy to treat persistent, progressive or relapsed disease, including the withdrawal of immunosuppressive therapy or donor lymphocyte infusion, will be considered evidence of relapse/progression. NRM will be considered a competing event.

7. Progression-Free Survival

The event for this endpoint is relapse/progression or death. The time to this event is measured from transplant to death or relapse/progression, whichever comes first. Patients who are alive and disease-free will be censored at last follow-up.

8. Overall Survival

The event for this endpoint is death from any cause. The time to this event is measured from the time of transplant to death from any cause or for surviving patients, to last followup. Survivors will be censored at last follow-up.

9. Pharmacokinetics and ADA/NAB testing

Pharmacokinetic sampling will be performed by Sun Pharmaceutical Industries Ltd., which will outsource these samples to Labcorp Drug Development. Given the long halflife of tildrakizumab, samples will be collected on week 0 (prior to administration of tildrakizumab), and then on days 30, 60, and 90. Each PK analysis draw requires five tubes of blood, each with 2-3 mL per tube, for a total of 10-15 mL of blood per PK analysis. PK samples should be stored at -70 degrees. Samples can be batched and shipped to Labcorp Drug Development.

MCW Protocol No: PRO00035737 24 Version No. 7 ADA testing is testing for anti-drug antibodies, while Nab testing is testing for neutralizing antibodies to give a more complete picture along with the PK testing. ADA testing typically includes 3 tiers- screen, confirm and titer where screen/confirm are qualitative (positive or negative) and titer is semi-quantitative. The Nab method for tildrakizumab is screen tier only and qualitative (positive or negative), in which only samples that test positive are confirmed in the ADA assay. The purpose of having ADA/Nab testing alongside the PK testing is to better understand the PK profile differences seen. For instance, if PK serum concentrations are lower for an individual then a high ADA response would provide more clarity regarding the serum levels. Nab testing then would give additional insight into the mode of action of the immunogenicity.

10. Incidence of infections

The incidence of grade ≥3 (CTCAE v5) viral, fungal, and bacterial infections will be determined. The cumulative incidence of CMV viremia post-alloHCT will be described.

11. Donor cell chimerism

Chimerism will be evaluated using sorted whole blood in CD3+ and CD33+ fractions. Mixed chimerism is defined as the presence of donor cells, as a proportion of total cells to be >5% and <95%. Full donor chimerism is defined as $\ge95\%$ of donor cells. Donor cells of $\le5\%$ will be considered as graft rejection. Donor cell chimerism will be assessed for all patients at day +28 (baseline) for both CD3+ and CD33+ fractions. The proportion of patients with each level of chimerism listed above will be described. CD3+ donor cell chimerism will be used to define the donor/recipient chimerism status.

12. Microbiome

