10 STATISTICAL CONSIDERATIONS

10.1 Study Endpoints

The endpoints are defined with more detail in Sections 2.3 through 2.5.

Primary endpoint

The primary endpoint is the 12-month probability of GVHD-free relapse-free survival (GRFS). An event for this outcome is defined as either grade III-IV acute GVHD, systemic therapy-requiring chronic GVHD, relapse, or death at 12 months.

MCW Protocol No: PRO00035737 44 Version No. 7 Version Date: 10/31/2022

Secondary endpoints

- 1. Cumulative incidence of mild, moderate and severe chronic GVHD according to the NIH criteria and limited or extensive GVHD by conventional criteria.
- 2. Cumulative incidence of grade II–IV acute GVHD at days 100 and 180.
- 3. Cumulative incidence of grade III–IV acute GVHD at days 100 and 180.
- 4. Incidence of primary and secondary graft failure.
- 5. Hematopoietic recovery will be assessed according to neutrophil and platelet counts recovery after HSCT.
- 6. Cumulative incidence of non-relapse mortality (NRM) post HSCT.
- 7. Cumulative incidence of relapse/progression of the primary malignancy.
- 8. Overall survival (OS) post HSCT.
- 9. Assess the pharmacokinetic (PK) profile of multi-dose tildrakizumab.
- 10. Probability of lower GI tract GVHD.

Exploratory endpoints

- 1. Longitudinal trajectory of serum cytokines.
- 2. Longitudinal trajectory of serum biomarkers.
- 3. Longitudinal trajectory of immune cell markers.

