10.3.2 Secondary Analysis (or Analysis of Secondary Endpoints)

The secondary endpoints will be evaluated in the efficacy analysis set. Time-to-event outcomes with and without competing risks will be analyzed using Kaplan-Meier and Nelson-Aalen estimates, respectively, and presented with 95% confidence intervals. Binary outcomes will be analyzed using proportions and presented with 95% confidence intervals.

Bacterial community composition will be characterized using OTU counts generated as described above. OTU counts will be converted to measures of relative abundance to account for variation in sequencing coverage between samples. Statistical analysis will be carried out using the statistical software package R (www.r-project.org). Alpha (α) diversity (richness and evenness of taxa within a population) will be reported using the Shannon Index⁴⁶ and Chao1 richness estimator. ⁴⁷ Beta (β) diversity (overlap in taxa shared between populations) will be analyzed using the Bray-Curtis dissimilarity metric⁴⁸ in conjunction with multivariate statistical analysis methods that will include Principal Components Analysis (PCA) and Permutational Multivariate Analysis of Variance (PERMANOVA).⁴⁹ Changes in abundance of individual taxa will also be analyzed using traditional univariate statistical methods.

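### No competing event is named for platelet recovery, and both estimators offered in 10.3.2 censor deaths, so recovery would be overstated by a small amount

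*Combined protocol and SAP*

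**What the plan says.** Section 2.5 item 4 covers both lineages under one heading. It defines neutrophil recovery, fixes the day of neutrophil engraftment, and then runs on to platelets: "The competing event is death without engraftment. Platelet recovery is defined by either the first day of a sustained platelet count". The platelet criterion is, more fully: "Platelet recovery is defined by either the first day of a sustained platelet count >20,000/mm³ for three days with no platelet transfusion". The item closes with "The first day of sustained platelet count above these thresholds will be designated the day of platelet engraftment". Nothing after the platelet definition mentions death, competing events or censoring.

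Section 10.1 lists the two lineages as one secondary endpoint, "Hematopoietic recovery will be assessed according to neutrophil and platelet counts recovery after HSCT", with no estimator.

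Section 10.3.2 chooses the estimator by whether competing risks are present: "Time-to-event outcomes with and without competing risks will be analyzed using Kaplan-Meier and Nelson-Aalen estimates, respectively, and presented with 95% confidence intervals". The Protocol Summary carries the same rule. Section 10.3.2 also sets the population: "The secondary endpoints will be evaluated in the efficacy analysis set". It does not mention platelet recovery or say which group it belongs to.

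**The concern.** A patient who dies before platelet recovery can no longer recover. An analysis that censors such a patient assumes recovery would have continued at the rate seen in patients still alive and unrecovered. One minus Kaplan-Meier then exceeds the proportion who actually recover. In the extreme, once every survivor has recovered, it reads 100% however many died first.

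The plan leaves the analyst without an instruction that avoids this. No competing event is named for platelets, and neither estimator in 10.3.2 treats death as competing. Hematopoietic recovery is a relevant safety description here: section 1.5 says the drug had not been tested for prevention or treatment of GVHD, and the run-in was built around engraftment. Both graft-failure definitions in 2.5 item 3 rest on neutrophils, so item 4 holds the only defined platelet-recovery endpoint.

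**Working it through.** **1. What the text assigns.** The documents give no expected platelet recovery figure, so there is none to reproduce.

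| Outcome | Competing event in 2.5 item 4 | Estimator under 10.3.2 as worded | Estimator if the order is reversed |
|---|---|---|---|
| Neutrophil recovery | Death without engraftment | Kaplan-Meier | Nelson-Aalen |
| Platelet recovery, if classed without competing risks | None named | Nelson-Aalen | Kaplan-Meier |
| Platelet recovery, if classed with competing risks | None named | Kaplan-Meier | Nelson-Aalen |

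Every cell in the last two columns holds an estimator that removes deaths from the risk set as censored. If a correction of 10.3.2 also brings in cumulative incidence for the competing-risk group, neutrophil recovery is repaired. Platelet recovery is repaired only if someone decides it belongs in that group, and 2.5 does not say so.

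**2. Largest possible gap.** Inputs: n = 55 enrolled (section 3.2), taken here as the efficacy set; d = deaths before platelet recovery. Kaplan-Meier passes each censored patient's weight of 1/55 to patients still at risk, so the overstatement cannot exceed d/55. It reaches d/55 when every survivor recovers:

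- cumulative incidence = 1 − d/55
- 1 − Kaplan-Meier = 100%
- SE = √[p(1 − p)/55], with p = 1 − d/55

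| d | Cumulative incidence | 1 − Kaplan-Meier | Gap (points) | Gap / SE |
|---|---|---|---|---|
| 1 | 98.2% | 100% | 1.8 | 1.0 |
| 2 | 96.4% | 100% | 3.6 | 1.4 |
| 3 | 94.5% | 100% | 5.5 | 1.8 |
| 5 | 90.9% | 100% | 9.1 | 2.3 |

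For d = 1: p = 54/55 = 0.982, SE = √(0.982 × 0.018/55) = 0.018, and the gap is 0.018, or 1.0 SE.

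The transform 1 − exp(−Nelson-Aalen) behaves almost identically in large samples. With 54 recoveries at distinct times its cumulative hazard is 1/54 + 1/53 + … + 1 ≈ 4.58, and 1 − exp(−4.58) ≈ 99.0%. So in a trial of this size it stops about one point short of 100%, but still above 98.2%.

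**3. Likely gap.** Section 10.5 expects 100-day mortality below 10%, so 10% is the top of the expected range. The documents give no recovery times, so those below are assumptions. The gap is 1 − Kaplan-Meier minus cumulative incidence at day 100.

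| Assumed recovery | Gap at 5% mortality | Gap at 10% mortality |
|---|---|---|
| Lognormal, median day 18 or 25; 0-10% never recover; exponential deaths | 0.9-1.4 points | 1.9-2.8 points |
| Lognormal, median day 20; 10-20% slow recoverers with median day 60; death hazard equal or tripled in slow recoverers | about 1.2-1.7 points | about 2.4-3.4 points |

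In the second row the gap is about 0.5-0.6 SE at 5% mortality and 0.9-1.1 SE at 10%, for n = 55. In the first row 1 − Kaplan-Meier and 1 − exp(−Nelson-Aalen) agree to three decimals.

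**The case against.** The strongest reply is that this is incomplete drafting and not a choice to censor deaths. The competing-event sentence sits under a heading shared by both lineages, refers to engraftment without saying neutrophil, and the same item later uses engraftment for platelets. Where the plan treats an outcome as free of competing risks, as for progression-free and overall survival, it writes a censoring rule, and platelet recovery has none. CMV viremia in item 10 also has no named competing event yet is described by cumulative incidence.

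Much of this stands. A reader might infer that the plan excludes death as a competing event for platelets, or prescribes that deaths be censored. The documents say neither: 2.5 is silent and 10.3.2 does not classify the endpoint. A reader might also infer that only platelets are affected, so that the two lineages would be reported on different estimands. The literal wording of 10.3.2 does not support that, because it gives Kaplan-Meier to outcomes with competing risks and so biases neutrophil recovery as well.

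The reply does not close the gap. The position of the sentence ties it to neutrophils. Even if it is shared, a patient whose neutrophils engraft and who then dies before platelet recovery has not plainly died without engraftment. Nor does putting platelets in the competing-risk group help while 10.3.2 names no estimator that treats death as competing.

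It is also fair to say that early deaths would not go unseen. Section 10.5 monitors 100-day mortality formally, 2.5 reports NRM at day 100 and overall survival, and section 7.2.1 sends grade 5 events to the DSMC within five calendar days.

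**Conclusion.** The concern holds as a gap in the endpoint definition combined with an unsuitable pair of estimators. It does not hold as a platelet-specific error that the plan prescribes. Followed as written, the plan overstates platelet recovery under either classification, and neutrophil recovery as well.

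The size is modest. The bound of about 1.8 points per death before recovery needs only n = 55, and it is a maximum. The range of roughly 1 to 3 points at 5-10% 100-day mortality depends on recovery times that are not in the documents. The endpoint is a descriptive secondary one; no test, stopping rule or decision uses it, and the primary GRFS analysis is unaffected. It should be corrected because the bias runs in the favourable direction on a safety-relevant outcome and is easily avoided.

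**What to change.** - **Section 2.5 item 4:** state that death without platelet recovery is the competing event for platelet recovery, and tie the existing sentence explicitly to neutrophils.
- **Section 10.3.2 and the Protocol Summary:** specify that neutrophil and platelet recovery are both estimated by cumulative incidence (Aalen-Johansen), at stated days such as 28 and 100, and correct the pairing of estimators with outcomes.
- **Same edit:** the platelet definition is worded as if it had alternatives and several thresholds but gives one, so complete it or remove that wording.

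The cost is a few sentences and a standard estimator, with no new data. Reported platelet recovery becomes slightly less favourable.
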